4.1.8.2 Presentation

The number and percentage of participants receiving prior or concomitant medication (by ATC4 classification system codes and generic name) will be presented by study intervention in separate tables for the FAS population. The number and percentage of participants receiving prior disease related medication will be presented by study intervention group for the FAS population by study intervention.

A separate table will be presented for participants who take restricted prior or concomitant medications. The numbers and percentages will be calculated relative to the number of participants in the FAS population by intervention group and overall.

All medications will also be listed by patient for the FAS population.

4.1.9 Substance usage – Inhaled Tobacco

4.1.9.1 Definitions and Derivations

Smoking status (cigarettes, cigars, pipes, smokeless tobacco and electronic nicotine delivery systems) together with the consumption of cigarettes in pack-years will be collected.

4.1.9.2 Presentation

All substance usage will be presented in summary tables for each study intervention group and overall. Smoking amount consumed in pack-years will be summarised descriptively as a continuous variable; all the other substance usage variables (i.e., substance type, substance usage) will be summarised as categorical variables with the number and percentage of participants by categories.

All substance usage will also be provided in listings.

The tables and the listings will be based on the FAS population.

4.1.10 Study Drug Compliance

4.1.10.1 Definitions and Derivations

Compliance with investigational product (IP) will be calculated using the following equation:

IP Compliance (%) =
$$\frac{Number\ of\ doses\ taken}{Number\ of\ intended\ doses} \times 100$$

The number of intended doses is equal to one tablet per day throughout the duration of the study for each patient, and thus it is approximated by treatment start date minus treatment end date +1, i.e. independent of any dose interruptions.

The number of doses taken is the "actual exposure" from section 4.7.1.1, i.e. the difference between dispensed and returned tablets as recorded in eCRF. If any 'Amount Returned' field in the Drug Accountability CRF page is blank, then the Number of Doses taken – and therefore IP Compliance – is not calculated.

Participants' IP compliance will be categorized in <80%, from 80% (included) to 120% (included), >120%. Participants having IP compliance between 80% to 120% inclusive will be defined as treatment compliant.

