
4 STUDY DESIGN

4.1 Overall Design

A schematic is provided in Section 1.2 showing the overall study design.

This is a Phase IIa, randomised, placebo-controlled, double-blind, parallel-arm, event-driven study with an up to 24-week treatment time. It will be performed in approximately 100 sites across approximately 14 countries. It is designed to evaluate the efficacy and safety of mitiperstat (AZD4831) administered QD using a tablet in adult participants with confirmed moderate to severe symptomatic COPD (FEV1/FVC < 0.7, \geq 10 pack-years smoking history, and post-BD FEV1 \geq 25% predicted) who are at high risk of exacerbations despite being maintained on optimised SoC inhaled therapies — triple inhaled therapy (ICS + LABA + LAMA) or ICS + LABA dual therapy or LABA + LAMA dual therapy for participants who are deemed unsuitable for ICS. The treatment will be over a minimum 12-week and maximum 24-week period.

- Approximately 677 participants will be screened and 406 participants randomised into the study to evaluate mitiperstat (AZD4831) 5 mg QD versus placebo.
- Being at high risk of exacerbations is defined as participants fulfilling one or more of the following criteria:
 - ≥ 1 moderate or severe exacerbation in the last 2 years (defined as requiring systemic corticosteroids and/or antibiotics for at least 3 days duration [or 1 injection of depot formulation], or hospitalisation for reason of AECOPD in the 24 months prior to screening; see Section 5.1).
 - Frequent productive cough (see Section 5.1).
 - Post-BD FEV1 of < 50% predicted.
- Participants will be randomised 1:1 to mitiperstat (AZD4831) 5 mg QD or placebo QD.
- Randomisation will be stratified by country.
- The primary objective is to evaluate the effect of mitiperstat (AZD4831) as compared to placebo on the time to first COPDCompEx event in patients with moderate to severe COPD. The primary endpoint will be time to first COPDCompEx event.
- Secondary assessments of efficacy include: time to first COPD exacerbation event, post-BD FEV1 at Week 12 compared to Week 1, MPO level and activity in sputum at Week 12 compared to baseline, and symptom scores.

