7.1.2 Temporary Discontinuation

Every attempt should be made to maintain participants on the study intervention during the course of the study. If the study intervention has been interrupted, it should be re-introduced as soon as, in the opinion of the investigator and the participant wishes to resume, the participant is able to re-start study treatment. The treatment period will not be extended to compensate for the temporary discontinuation. Note related to AESI skin reactions (including maculopapular rash): In the occurrence of maculopapular rash CTCAE Grade 1, 2, and 3, or generalised rash/skin reaction without an alternative suspect COPD medication (per Section 7.1.1), or serious rash/skin reaction, study intervention should be permanently discontinued.

At each visit, participants will be instructed to stop the study intervention and contact the investigator immediately if rash or skin reaction has developed. If, after the participant has

been seen by the study doctor or designee, the skin reaction does not meet permanent discontinuation criteria per Section 7.1, the study treatment can be restarted.

In the event that a participant develops symptoms suggestive of COVID-19 infection, the participant should undergo confirmatory rapid screening test for SARS-CoV-2 or PCR testing as soon as possible. Rapid screening test could be either lateral flow test/antigen test or molecular test. If the rapid screening test or PCR test confirms COVID-19 infection, the study intervention should be immediately discontinued on a temporary basis, unless any permanent discontinuation criteria are met (Section 7.1). After discontinuation of study intervention, any appropriate treatment is allowed if conditions presented in Section 6.9 are met.

In the event that a participant develops symptoms suggestive of pneumonia, the participant should undergo confirmatory chest x-ray and appropriate blood testing (eg, hsCRP, complete/full blood count, procalcitonin as deemed appropriate by the investigator) as soon as possible. If chest x-ray confirms the presence of consolidation and clinical markers are consistent with acute infection, the study intervention should be immediately discontinued on a temporary basis, unless any permanent discontinuation criteria are met (Section 7.1). After discontinuation of study intervention, any appropriate treatment is allowed if conditions presented in Section 6.9 are met.

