In cases of 'unconfirmed pneumonia', if the participant is not hospitalised and/or does not have a chest x-ray confirming diagnosis of pneumonia, this should generally be considered an infective exacerbation of COPD rather than pneumonia. In this scenario, study intervention can continue. If the investigator still considers this to be pneumonia, then discussion with the AstraZeneca medical monitor would be needed regarding continuation/discontinuation of study intervention.

In case of serious infection, the study intervention should be immediately discontinued on a temporary basis, unless any permanent discontinuation criteria are met (Section 7.1). After discontinuation of study intervention, any appropriate treatment is allowed if conditions presented in Section 6.9 are met.

Study intervention does not need to be stopped for antibiotic treatment of non-serious infection.

If a participant does not receive study intervention for ≥ 28 days continuously, they should be permanently withdrawn from the study intervention.

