4.7.1 Exposure

4.7.1.1 Definitions and Derivations

Exposure duration is calculated only for participants in the Safety population as the total number of days on study drug and is calculated as:

Exposure duration (days) = Last drug application date -First drug application date + 1 - (treatment interruption period)

The date from end of treatment phase is to be used for last drug application date.

Exposure as measured by amount tablets administered calculated as:

 $Actual\ exposure\ (tablets) = tablets\ dispensed-tablets\ returned$

Note that if any 'Amount Returned' field in the Drug Accountability CRF page is blank, then this formula will not be calculated.

If any of the first or last dates are missing or partially missing, then imputed dates will not be used, and study drug exposure is set to missing.

Total amounts of doses received will be calculated as number of days where at least one dose amount of >0 is administered. The first dose of the intervention period intended to be the SV3 dose and the intended last dose of the intervention period is SV7 dose.

Total time of exposure (patients-years) is calculated as:

Total time of exposure (patients – years) =
$$\frac{1}{365.25} \times \sum_{Patient} Exposure duration$$

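### The intended-doses formula in SAP 4.1.10.1 has its dates reversed, so read literally almost every fully adherent participant gets a negative compliance score and is classed below 80%

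*SAP*

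**What the plan says.** SAP 4.1.10.1 defines compliance as 100 times the number of doses taken over the number of intended doses.

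- **Numerator:** tablets, counted as "the difference between dispensed and returned tablets as recorded in eCRF".
- **Denominator in words:** "The number of intended doses is equal to one tablet per day throughout the duration of the study for each patient".
- **Denominator as a formula:** "it is approximated by treatment start date minus treatment end date +1, i.e. independent of any dose interruptions".
- **Classification:** three categories, <80%, 80% to 120%, and >120%. "Participants having IP compliance between 80% to 120% inclusive will be defined as treatment compliant".

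SAP 4.1.10.2 summarises the result by arm on the Full Analysis Set, and Appendix B lists it as Table 14.1.18.

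The related exposure derivation in SAP 4.7.1.1 has the dates in the usual order and subtracts interruptions: "Last drug application date -First drug application date + 1 - (treatment interruption period)".

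On interruptions, Protocol 7.1.2 says for confirmed COVID-19, confirmed pneumonia and serious infection that "the study intervention should be immediately discontinued on a temporary basis", and it does not extend the treatment period to make up the time. Protocol 7.1.3 sets the earliest restart at 7 days after the COVID-19 test, or 7 days after antimicrobial treatment ends for pneumonia or serious infection.

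**The concern.** A derivation in a SAP should give the right answer when programmed as written. This one does not: start minus end is negative for any ordinary course, and adding 1 does not rescue it. The literal formula also reverses the ranking, because a participant who takes fewer tablets gets a score closer to zero.

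What is at stake is the planned compliance table, which readers would consult when interpreting a null or weak efficacy result. The amendment history in the SAP records an update to the compliance calculation dated 10/3/2024, so the reversed order stands in the text after the most recent logged edit to this calculation.

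A second question is how the section treats required interruptions. Days on which the protocol stops dosing stay in the denominator, while no tablets can be added to the numerator on those days.

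**Working it through.** The documents give no numeric compliance figure to reproduce, so this is direct arithmetic on the formula.

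**Inputs**
- Course length D: 84 to 168 days (Protocol 4.1: "The treatment will be over a minimum 12-week and maximum 24-week period"), with shorter courses for early discontinuation.
- Limits for compliant: 80% to 120% inclusive (SAP 4.1.10.1).
- Longest single interruption that still allows restart: 27 days. Protocol 7.1.2 requires permanent withdrawal from study intervention at 28: "If a participant does not receive study intervention for ≥ 28 days continuously".

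**Step 1: the formula as written.** With start on Day 1 and end on Day D, the denominator is 1 - D + 1 = 2 - D. With every tablet taken, compliance is 100 × D / (2 - D).

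| D (days) | Denominator as written | Compliance as written | End - start + 1 | Compliance with that denominator |
|---|---|---|---|---|
| 1 | 1 | 100% | 1 | 100% |
| 2 | 0 | undefined | 2 | 100% |
| 3 | -1 | -300% | 3 | 100% |
| 28 | -26 | -107.7% | 28 | 100% |
| 84 | -82 | -102.4% | 84 | 100% |
| 168 | -166 | -101.2% | 168 | 100% |

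The denominator is negative from 3 days of treatment onward, so these participants all fall in <80%. The ranking reverses too: over 84 days, taking half the tablets gives 42 / (-82) = -51.2%, which is higher than the -102.4% for full adherence.

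**Step 2: dates corrected, interruptions left in the denominator.** A participant who takes every permitted tablet but is off drug for g days scores 100 × (D - g) / D.

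| Days off (g) | D = 84 | D = 168 |
|---|---|---|
| 7 | 77/84 = 91.7% | 161/168 = 95.8% |
| 14 | 70/84 = 83.3% | 154/168 = 91.7% |
| 16 | 68/84 = 81.0% | 152/168 = 90.5% |
| 17 | 67/84 = 79.8% | 151/168 = 89.9% |
| 21 | 63/84 = 75.0% | 147/168 = 87.5% |
| 27 | 57/84 = 67.9% | 141/168 = 83.9% |

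Falling below 80% takes at least 17 days off in 84, 23 in 112, 26 in 126, or 34 in 168. A single restartable stop (27 days at most) can do it only when the course is 134 days or shorter: 107/134 = 79.9%, but 108/135 = 80.0%.

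**Step 3: a pneumonia stop.** The documents do not give the length of an antimicrobial course. Assuming 7 to 14 days plus the 7-day wait, and counting the stop from the start of the course, dosing stops for 14 to 21 days. That gives 83.3% to 75.0% over 84 days and 91.7% to 87.5% over 168 days.

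**The case against.** The strongest reply on the dates is that this is an evident slip. The same sentence states the intended meaning, SAP 4.7.1.1 has the right order, and a program that returned negative percentages for nearly everyone would be noticed at once. That is a fair account of the likely outcome, but it does not make the text correct.

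On interruptions, the SAP is explicit that it ignores them. Tablets taken against an uninterrupted schedule is a legitimate measure, so that part is a choice to explain and not a mistake. This stands.

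A reader might infer more than the documents support:

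- **That participants who follow the protocol are generally classed as non-compliant once the dates are corrected.** A 7-day stop stays compliant at either course length, and no single restartable stop in a 168-day course goes below 83.9%.
- **That the SAP uses two conflicting compliance denominators.** Exposure duration in SAP 4.7.1.1 counts days on drug, a different quantity. Compliance borrows only the tablet count from that section.
- **That Table 14.1.18 is the only adherence evidence.** The SAP also plans exposure net of interruptions (Table 14.3.1.1), amount administered (Table 14.3.1.2), adverse events leading to dose interruption by arm (Table 14.3.2.1), Week 12 plasma concentrations (Table 14.2.3.1) and a listing of administration (Appendix 16.2.5).
- **That the table will show a false imbalance between arms.** Infection is a potential risk of the drug in Protocol 2.3.1, but the same table says no increase has been seen. Unequal stops are possible; the documents do not show that they will occur.

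**Conclusion.** The intended-doses formula is wrong as written. Applied literally, it gives a negative denominator for anyone treated 3 days or more and classes fully adherent participants as <80%, at -102.4% for 84 days and -101.2% for 168 days. It is not wrong for every conceivable participant: one day of treatment gives 100%, and two days gives an undefined value.

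The treatment of interruptions is not an error. After the dates are corrected, it matters only for a stop of 17 to 27 days in a course near 12 weeks, or for repeated stops. How often that will happen cannot be worked out from the documents. These percentages assume that every permitted tablet is taken and that the tablet count is complete.

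The consequence is small. Compliance is only tabulated, and SAP Section 2 drops the Per-Protocol Set, so no endpoint, analysis set, alpha or power depends on it.

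**What to change.** **Required.** In SAP 4.1.10.1, define intended doses as treatment end date minus treatment start date + 1. This changes one line, uses dates the derivation already needs, and has no downside.

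**Optional, for clarity.** Add a sentence saying that compliance is measured against the uninterrupted schedule and is therefore not a measure of adherence to the protocol's stopping rules. Show days of interruption, as derived in SAP 3.3.1.2, in a separate row of Table 14.1.18. The cost is one sentence and one table row: Protocol 6.5 already has the dates of intervention delays recorded in the eCRF. Total interruption days are enough. Splitting them into protocol-required and other would need a classification that the documents do not show is collected.

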4.1.10.2 Presentation

The compliance with IP will be presented in a summary table for each study intervention group and overall.

The number and percentage of participants by each compliance category will also be provided.

The tables will be based on the FAS population.

4.2 Endpoint Analyses

This section covers details related to the endpoint analyses such as primary, secondary, other endpoints including sensitivity and supportive analyses.

All endpoint analyses will include data reported up to end of treatment (EOT) visit.

Table 9 Analyses of primary, secondary and tertiary/exploratory endpoints

Objectives	Estimand description / Outcome Measure	Population
Primary		
To evaluate the effect of AZD4831 as compared to placebo on the time to first COPDCompEx event in participants with moderate to severe COPD.	Endpoint: time to first COPDCompEx event. Population level-summary measure: hazard ratio. Strategy for intercurrent events: Primary estimand: while on treatment. Supportive estimand: treatment policy.	FAS
Secondary		
To assess the PK of AZD4831 in participants with moderate to severe COPD.	Endpoint: plasma AZD4831 concentration-time profiles during the intervention and follow-up periods, and PK parameters. Population level-summary measure: summary statistics. Strategy for intercurrent events: while on treatment.	PK set

Objectives	Estimand description / Outcome Measure	Population
To evaluate the effect of AZD4831 as compared to	Endpoint: time to first COPD exacerbation event ^a	FAS
placebo on the time to first	Population level-summary measure:	
moderate or severe COPD	hazard ratio.	
exacerbation.	Strategy for intercurrent events: while on treatment.	
To assess the effects of AZD4831 as compared to	Endpoint: change from baseline in post-BD FEV1 after 12 weeks.	FAS
placebo on post-BD FEV1 in	Population level-summary measure: the	
participants with moderate to	difference in mean.	
severe COPD.	Primary	
	estimand: while on treatment.	
	Supportive estimand: treatment policy.	
To assess the effect of AZD4831 compared with placebo on respiratory symptoms in participants with moderate to severe COPD.	Endpoint: change from baseline in EXACT, BCSS average score, and Cough VAS average score at Week 12 and Week 24. Population level-summary measure: the	FAS
	difference in mean.	
	Strategy for intercurrent events: while on treatment.	
To assess the effect of AZD4831 compared with	Endpoint: change from baseline in Total CAT measured in clinic at Week 12.	FAS
placebo on disease impact in	Population level-summary measure:	
participants with moderate to	The difference in mean.	
severe COPD.	Proportion of participants with change from baseline of -2 or less	
	Strategy for intercurrent events: while on treatment.	
Safety		
To assess the safety and tolerability of AZD4831 compared with placebo in participants with moderate to severe COPD.	Endpoint: safety and tolerability evaluations using AEs, SAEs, AESIs (skin reactions, including maculopapular rash, and serious infections, including pneumonia), vital sign measures, clinical	SS

Objectives	Estimand description / Outcome Measure	Population
	laboratory assessments (clinical chemistry, haematology, and urinalysis), and ECG.	
	Population level-summary measure:	
	descriptive statistics eg, absolute counts and frequencies.	
Tertiary/Exploratory		
To assess the effect of AZD4831 compared with placebo on biomarkers related to COPD disease activity.	Systemic biomarkers of cardiovascular comorbidities - including fibrinogen, hsCRP, IL-6, and NT-proBNP.	FAS
To assess the effects of AZD4831 as compared to placebo on MPO activity and concentration in sputum samples from participants with moderate to severe COPD.	Average change from baseline to Week 12 in MPO activity normalised to MPO concentration in sputum.	FAS
To assess the effects of AZD4831 as compared to placebo on spirometry endpoints measured face-to-face in participants with moderate to severe COPD.	Spirometry endpoints, including but not limited to, FEV1, forced vital capacity, forced expiratory flow 25% to 75%, inspiratory capacity, and reproducibility.	FAS
To assess the effect of sputum MPO concentration at baseline on primary and secondary endpoints in participants with moderate to severe COPD.	Time to first COPDCompEx event in participants with low MPO concentration at baseline compared to high MPO concentration at baseline. Change from baseline post-BD FEV1 in participants with low MPO concentration	FAS
	at baseline compared to high MPO concentration at baseline.	
To assess the effects of AZD4831 compared to placebo on change in cough frequency measured over a	Change from start of treatment in average 24-hour, waking, and sleeping cough frequency, using the VitaloJAK® Cough Monitor device, at Week 12.	Cough subset

Objectives	Estimand description / Outcome Measure	Population
24-hour period between start of treatment and Week 12.		
To investigate whether cough frequency is associated with lung function (eg, PEF, FEV1), cough/COPD symptom scores (eg, BCSS, CAT and Cough VAS) and blood biomarkers (eg, MPO concentration).	Average cough frequency measured over a 24-hour period as measured at start of treatment (Visit SV3) and after 12 weeks treatment (Visit SV5) using the VitaloJAK Cough® Monitor device.	Cough subset
To assess the effects of AZD4831 as compared to placebo on COPDCompEx in participants with moderate to severe COPD.	Annualised rate of COPDCompEx events, based on the period from baseline to the last dose Strategy for intercurrent events: while on treatment.	FAS
To assess the effect of AZD4831 compared with placebo on moderate to severe COPD exacerbation.	Annualised rate of moderate or severe COPD exacerbations based on the period during the intervention from baseline to the last dose Strategy for intercurrent events: while on treatment.	FAS

COPD Exacerbation: a worsening in the participant's usual COPD symptoms that is beyond normal day-to-day variation, is acute in onset, lasts 2 or more days (or less if the worsening is so rapid and profound that the treating physician judges that intensification of treatment cannot be delayed), may warrant a change in regular medication, and leads to any of the following:

- Use of systemic corticosteroids for at least 3 days; a single depot injectable dose of corticosteroids will be considered equivalent to a 3-day course of systemic corticosteroids.
- Use of antibiotics to treat COPD exacerbation for at least 3 days.
- An inpatient hospitalisation due to COPD (defined as an inpatient admission ≥ 24 hours in the hospital, an observation area, the emergency department, or other equivalent healthcare facility depending on the country and healthcare system).
- Admission in emergency department or emergency room due to COPD for < 24 hours requiring intensive treatment.
- Results in death.

Intercurrent events are events occurring after treatment initiation (eg, premature treatment discontinuation, switching treatment, terminal events such as death) that affect either the measurement or interpretation of the summary measure (eg, hazard ratio) associated with the clinical question of interest. This study contains 2 intercurrent events:

- 1 Premature treatment discontinuation (with the following reasons: SAE, death not due to exacerbation, COVID-19, pneumonia, other).
- 2 Prohibited medication.

